## 10. Safety

All analyses described in this section will be performed using the SAF. The results will be descriptive in nature. All data will be summarized and listed.

[figure not shown]
Safety will be assessed on the basis of AEs, laboratory parameters (routine safety and intravascular hemolysis), vital signs, and physical examination.

### 10.1. Extent of Exposure

#### 10.1.1. Overall

The duration of exposure will be expressed as the time in weeks from the first infusion of Klg10 through to the last visit (inclusive), with treatment administration and will be summarized.

The total number of administered infusions will be summarized for continuous variable and by categorizing the data according to the following categories:

The actual calculated dose in mg/kg, based on the total dose administered and body weight at a given visit, will also be calculated at each infusion. The actual dose in mg/kg, the actual dose in mg and ml, number of patients with dose modification or dose interruption will be summarized for each infusion together with the reason for changes in the dose. Changes of planned infusion rate [ml/kg/min] during any infusion and the reason for change will be summarized. In addition, the total dose administered in mg and ml across all infusions will be summarized.

Duration of infusion in min will also be summarized for each infusion.

All data will be presented overall and by infusion schedule.

Additionally, extent of exposure will be presented for age categories defined in the [Section 6.6.1](#).

All available information will be listed.

#### 10.1.2. AE related

The following information will be summarized overall and by infusion schedule:

- Number and proportion of Klg10 infusions for which the infusion rate is decreased due to AEs (from infusion 1 to infusion 17)
- Number and proportion of Klg10 infusions with 1 or more infusional (temporally-associated) AE (from infusion 1 to infusion 17).
- A 1-sided 95% confidence interval (CI) will be produced for the proportion of infusions with 1 or more temporally-associated AEs (including AEs determined not to be product-related) using an exact binomial method. Due to the clustered nature of the data, a Design Effect will be applied to the confidence interval. An analysis of variance method will be used to calculate the Intra Cluster Correlation Coefficient (5).

For this analysis, safety will be declared if the upper 1-sided 95% confidence is less than 0.4 (counting overall infusions).

This document is confidential.

For producing such CI the following steps will be performed:

**1 Calculate the raw 1-sided 95% CI:** This will be done using an exact binomial method (e.g. Clopper Pearson)

**2 Calculate the intraclass correlation coefficient:** The point estimate via ANOVA method is given by Wu (5) as:

$$\widehat{\rho}_A = \frac{MSB - MSW}{MSB + (n_A - 1) * MSW}$$

where

$$n_A = \frac{1}{(k - 1)} \left( N - \frac{\sum n_i^2}{N} \right)$$

$$MSB = \frac{1}{(k - 1)} \left( \sum \frac{Z_i^2}{n_i} - \frac{(\sum Z_i)^2}{N} \right)$$

$$MSW = \frac{1}{(N - k)} \left( \sum Z_i - \sum \frac{Z_i^2}{n_i} \right)$$

and

MSB and MSW: between-group and within-group mean squares from a one-way analysis of variance of the binary data

k: number of clusters (patients)

ni : number of observations (infusions) on the ith cluster (patient)

Yij: the response of patient j in cluster i (with Yij: 0 meaning negative to the event of interest and Yij: 1 meaning positive to the event of interest where the event of interest having at least one associated infusional Adverse Event). The sum Yij is equal to the number of successes on the ith cluster and it is labelled as Zi i.e.

$$Z_i = \sum_j Y_{ij}$$

N is the number of total observations (infusions) in the considered analysis i.e.

$$N = \sum n_i$$

**3 Calculate the Design Effect:** A conservative approach is given by Eldridge (6). The Design effect can be written as:

$$DE = 1 + \left( \left[ \left\{ cv^2 \frac{(k - 1)}{k} + 1 \right\} * \bar{m} \right] - 1 \right) * \widehat{\rho}_A$$

This document is confidential.

Where:

cv: ratio of the standard deviation of cluster sizes  $s_m$  to the mean cluster size,  $\bar{m}$

$$s_m^2 = \frac{\sum(m_i - \bar{m})^2}{(k - 1)}$$

$m_i$ : size of the cluster  $i$

$k$ : number of clusters

$\hat{\rho}_A$ : calculated in step 2

**4 Apply the Design Effect to the CI:** Upper Confidence Limit to be reported = Design effect \* Upper Confidence Limit (from exact binomial)

At the DRM prior to database lock it will be evaluated if other methods that take in account the clustered nature of the data should be performed (e.g., Generalized Estimating Equation).

The raw CI and the results of the supportive analyses that take the clustering into account will be reported.

All available information will be listed.

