#### 6.6. Subgroups

Subgroup analyses by age and treatment schedule are planned to be performed for the primary and secondary efficacy endpoints and for safety endpoints, including AEs (infusional AEs and treatment-emergent AEs). Additional subgroup analyses by sex, race are planned to be performed for the primary efficacy endpoint. Subgroup analysis by region will not be performed because only sites of USA enrolled subjects.

This document is confidential.

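### SAP 10.1.2 sets no floor at zero on the ANOVA intraclass correlation, so a negative estimate makes the clustering adjustment tighten the upper limit for infusions with an adverse event

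*SAP*

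**What the plan says.** On the clustering adjustment, SAP 10.1.2 states: "An analysis of variance method will be used to calculate the Intra Cluster Correlation Coefficient". It then builds the limit in four steps. Step 1 takes the one-sided 95% exact (Clopper-Pearson) upper limit over infusions. Step 2 estimates the intraclass correlation: "The point estimate via ANOVA method" is (MSB − MSW)/(MSB + (n_A − 1)·MSW). Step 3 computes the design effect, introduced with "A conservative approach is given by" a cited source, and takes the correlation as "calculated in step 2". Step 4 reads "Upper Confidence Limit to be reported = Design effect" times the exact upper limit.

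The result feeds a decision: "safety will be declared if the upper 1-sided 95% confidence is less than 0.4", counted over all infusions. Protocol 10.4.3 states the same rule. The SAP asks for the output overall and by infusion schedule. It also reports the raw interval, and leaves other cluster methods to the data review meeting.

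Neither document puts a lower bound on the correlation or the design effect, or says what to do with a negative estimate.

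**The concern.** The adjustment exists because infusions within a patient are correlated, which normally means that the naive limit is too tight. An estimator that can go negative, used without a bound, can turn the adjustment the other way and give a limit below the one that ignores clustering altogether. The limit decides a pre-specified safety declaration, so an error in that direction can only make the declaration easier to reach.

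**Working it through.** The plan gives no calculated figure for the 0.4 rule, so there is none to reproduce. The check takes the SAP formulas as written.

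**Algebra.** Step 3 is DE = 1 + ([{cv²(k − 1)/k + 1}·m̄] − 1)·ρ̂, with m̄ the mean number of infusions per patient. The schedules give 13 infusions (28-day) or 17 (21-day), so the factor multiplying ρ̂ is well above zero. Hence MSB < MSW gives ρ̂ < 0, then DE < 1, then DE × limit < limit.

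**Worked example.** Take 40 patients (SAP 3.6, minimum evaluable) with 13 infusions each, N = 520. The event counts are illustrative: eight patients each with 3, 4, 5, 6 and 7 affected infusions.

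- ΣZ = 8 × 25 = 200, an observed proportion of 200/520 = 0.385. The exact 95% upper limit is 0.421, which fails 0.4.
- ΣZ²/n = 8 × (9 + 16 + 25 + 36 + 49)/13 = 1080/13 = 83.08, and (ΣZ)²/N = 40000/520 = 76.92.
- MSB = (83.08 − 76.92)/39 = 0.158. MSW = (200 − 83.08)/480 = 0.244. Equal cluster sizes give n_A = 13 and cv = 0.
- ρ̂ = (0.158 − 0.244)/(0.158 + 12 × 0.244) = −0.028.
- DE = 1 + 12 × (−0.028) = 0.67 (0.666 before rounding).
- Reported limit = 0.666 × 0.421 = 0.280. This passes 0.4 and lies below the observed 0.385.
- With ρ̂ set to 0, DE = 1, the limit is 0.421 and the rule is not met.

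**How often.** The documents give no true correlation, event proportion or schedule mix, so these are assumed. The table comes from beta-binomial simulation of the SAP steps with 45 patients, half on 13 and half on 17 infusions. The documents give at least 40 evaluable and about 50 screened; 45 is an assumption between them.

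| True correlation | Chance of a negative estimate | Safety declared at true proportion 0.40, as written | Same, with floor |
|---|---|---|---|
| 0 | about 0.52 | 0.39 | 0.025 |
| 0.02 | 0.13 to 0.15 | 0.08 | 0.01 |
| 0.05 | 0.01 | 0.006 | 0.003 |
| 0.10 or more | about 0 | essentially no difference | essentially no difference |

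For comparison, the unadjusted exact limit meets the rule about 5% of the time at a true proportion of 0.40 and correlation 0. At true proportions of 0.2 to 0.3 the chance of meeting the rule is the same with and without the floor. With 40 patients the picture is similar: a negative estimate has chance 0.52 to 0.54 at correlation 0, 0.15 to 0.20 at 0.02 and 0.01 to 0.03 at 0.05.

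In a group of 12 patients a negative estimate is more frequent: about 0.33 at correlation 0.02, 0.14 at 0.05 and 0.04 at 0.10.

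**How much belongs to step 4.** Suppose the design effect were applied to the sample size (N/DE) instead of to the limit. With 45 patients and a true proportion of 0.40, safety would be declared 0.051 of the time without a floor and 0.043 with it at correlation 0, 0.043 and 0.042 at 0.02, and 0.048 in both cases at 0.05. When the estimate is negative, the limit would fall below the exact limit by a median of 0.001 to 0.002 with 45 patients and 0.005 to 0.010 with 12.

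**The case against.** The strongest reply is that the harm comes from step 4. The figures above bear this out: with the design effect applied to the sample size, the missing floor hardly moves the error rate at 45 patients. What remains is the direction. A design effect below 1 still gives a limit tighter than the exact one under either use, so correcting step 4 shrinks the problem without removing it.

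Second, the overall decision is sensitive only in a corner, with a true proportion near 0.4 and almost no within-patient correlation. That stands. The documents do not say whether the trial will be in that corner.

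Third, a reader might infer from SAP 6.6 ("Subgroup analyses by age and treatment schedule are planned to be performed for the primary and secondary efficacy endpoints and for safety endpoints") that this limit will be produced for the small pediatric age groups and will often be too low there. The documents do not support that reading. SAP 10.1.2 asks for it overall and by infusion schedule, while neighboring sections name age categories where they are wanted. The 0.4 rule counts overall infusions, so no decision attaches to a subgroup. Even with 12 patients, a negative estimate is infrequent once the correlation reaches 0.05 to 0.10.

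Fourth, the raw interval is reported alongside, so a limit below it would be visible, and the data review meeting may consider methods such as generalized estimating equations. Both help, but neither says which limit governs the declaration.

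Finally, the SAP's word conservative describes the cited design-effect formula. It does not promise a design effect of at least 1.

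**Conclusion.** The gap is real and follows from the formulas alone: no floor is written, and a negative estimate necessarily gives a reported limit below the unadjusted exact limit. Its weight is small. The overall declaration changes materially only if the true proportion is near 0.4 and the correlation is about 0 to 0.02; at correlations of 0.10 or more, or proportions of 0.2 to 0.3, it does not. These sizes rest on assumed correlations, proportions and group sizes.

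For the by-schedule intervals it matters if one schedule group turns out small. For age groups it matters only if the interval is also produced by age, which SAP 10.1.2 does not state.

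A reader might also conclude that the missing floor alone explains limits below the observed proportion, or that the trial's safety conclusion is unsound. Neither follows. Such limits arise from step 4 multiplying the limit itself, and the documents give no ground for expecting the near-zero correlation and near-0.4 proportion that would be needed to alter the declaration.

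**What to change.** In SAP 10.1.2 step 3, replace the correlation by max(0, ρ̂_A), so that the design effect is at least 1 wherever this interval is produced. The reported limit then cannot fall below the raw exact limit.

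The cost is one line in the SAP and one in the program. The limit is wider only when the estimate is negative, and is otherwise unchanged. The change does not correct step 4, which needs its own amendment. Both are best settled before database lock, so that the choice of governing limit is not made with the data in view.

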##### Safety Objective

To assess the safety of Klg10 in the overall study population from day 1 to week 51/52.

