### **Analysis**

Secondary safety endpoints will be summarized using descriptive statistics. Additionally, a 1-sided 95% CI will be produced for the proportion of infusions with 1 or more temporally-associated AEs (including AEs determined not to be product-related) using an exact binomial method. Due to the clustered nature of the data, a Design Effect will be applied to the confidence interval. An analysis of variance method will be used to calculate the Intra Cluster Correlation Coefficient (Wu, 2012). For this analysis, safety will be declared if the upper 1-sided 95% confidence is less than 0.4. Other methods that take in account the clustered nature of the data could be performed (e.g., Generalized Estimating Equation). Additionally, a 2-way table will summarize the frequency and proportion of infusion related AE by speed of infusion category. This table will be produced overall and by the number of infusional related AE experienced per patient (e.g., 1 event experienced, 2 events experienced, 3+ events experienced).

Further details will be provided in the SAP.

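### SAP 10.1.2, step 4 multiplies the exact binomial upper limit by the design effect, so the figure compared with 0.4 to declare safety is not a 95% upper limit

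*SAP*

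**What the plan says.** Protocol 10.4.3 (Analysis) and SAP 10.1.2 set the same rule. A 1-sided 95% exact binomial interval is formed for the proportion of infusions with at least one temporally associated AE, related or not, and is then adjusted for repeated infusions within a patient. The SAP states that "safety will be declared if the upper 1-sided 95% confidence is less than 0.4 (counting overall infusions").

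The protocol does not say how the adjustment works, only: "Due to the clustered nature of the data, a Design Effect will be applied to the confidence interval". The SAP does, in four steps introduced by "For producing such CI the following steps will be performed":

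1. the raw Clopper-Pearson limit;
2. an ANOVA estimate of the ICC;
3. a design effect that allows for unequal numbers of infusions per patient;
4. "Upper Confidence Limit to be reported = Design effect \* Upper Confidence Limit (from exact binomial").

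The SAP sets no floor on the ICC or on DE and no cap on the resulting limit. After step 4 it adds that at the data review meeting "it will be evaluated if other methods that take in account the clustered nature of the data should be performed", and that "The raw CI and the results of the supportive analyses that take the clustering into account will be reported". Neither is linked to the 0.4 criterion.

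**The concern.** DE states how much clustering inflates the variance of the estimated proportion. It therefore belongs on the sample size (N/DE) or, as its square root, on the distance from the estimate to the limit. Step 4 applies it to the limit itself. Writing the raw limit as U = p + (U − p) gives DE × U = DE × p + DE × (U − p). The centre is moved from p to DE × p, and the margin is stretched by DE where √DE is wanted.

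The error can go either way. With positive clustering the limit is too high. With almost none, the ANOVA estimate is often negative, DE falls below 1, and the reported upper limit can lie below the observed proportion.

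This is the only numeric criterion in the documents for declaring safety. Protocol 3.1 lists safety among the primary objectives, to be assessed "in the overall study population from day 1 to week 51/52".

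**Working it through.** **Inputs from the documents.** 1-sided 95%, Clopper-Pearson, threshold 0.4 (SAP 10.1.2); at least 40 evaluable patients (SAP 3.6); 13 infusions on the 28-day schedule or 17 on the 21-day schedule (SAP 3.4). The plan gives no power, expected proportion or ICC for this rule, so it has no figure of its own to reproduce.

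**Assumptions.** 30 patients with 13 infusions and 10 with 17, so N = 390 + 170 = 560 and mean cluster size 14. ICC and the AE proportion are varied.

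**Design effect (SAP step 3).** Variance of cluster sizes = (30 × 1² + 10 × 3²)/39 = 3.077, so cv² = 3.077/14² = 0.0157. DE = 1 + ([0.0157 × 39/40 + 1] × 14 − 1) × ICC = 1 + 13.21 × ICC.

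**One case in full.** Observed 0.20 (112/560): raw limit 0.230. At ICC 0.1, DE = 2.321.

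- SAP step 4: 2.321 × 0.230 = 0.534.
- Clopper-Pearson on x/DE and N/DE: 0.247.
- Square-root check: 0.20 + √2.321 × 0.030 = 0.246, in line with the effective-N limit.

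**Fixed examples.**

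| Observed | ICC | SAP limit | Effective-N limit |
|---|---|---|---|
| 0.10 | 0.05 | 0.205 | 0.131 |
| 0.10 | 0.1 | 0.286 | 0.138 |
| 0.10 | 0.2 | 0.449 | 0.149 |
| 0.20 | 0.02 | 0.291 | 0.234 |
| 0.20 | 0.05 | 0.382 | 0.239 |
| 0.20 | 0.1 | 0.534 | 0.247 |
| 0.20 | 0.3 | 1.141 | 0.272 |

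**Break-even ICC** = (0.4/raw limit − 1)/13.21. The SAP limit exceeds 0.4 above ICC 0.37, 0.17, 0.095, 0.056, 0.032 and 0.015 at observed 0.05, 0.10, 0.15, 0.20, 0.25 and 0.30. The effective-N limit stays below 0.4 at every ICC for observed 0.25 or less, and up to ICC 0.50 at observed 0.30.

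**Negative ICC estimate.** At observed 0.20 and estimated ICC −0.02, DE = 1 − 0.264 = 0.736 and the reported upper limit is 0.736 × 0.230 = 0.169, below the observed 0.20.

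**Simulation** of SAP steps 1 to 4 on beta-binomial data, 20,000 trials per cell. Chance of declaring safety under the SAP rule:

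| True proportion | ICC 0.05 | ICC 0.1 | ICC 0.2 |
|---|---|---|---|
| 0.05 | 100% | 99% | 87% |
| 0.10 | 99% | 87% | 44% |
| 0.20 | 61% | 18% | 2% |
| 0.30 | 10% | 1% | 0% |

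The effective-N limit gives about 100% in the first three rows and 98%, 93% and 80% in the last.

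**Near-zero ICC.** At a true proportion of 0.40, safety is wrongly declared in 39%, 20%, 10% and 1% of trials at ICC 0, 0.01, 0.02 and 0.05, against 4 to 5% with effective N. At ICC 0 the SAP limit covers the true value in 84%, 77%, 69% and 61% of trials at true 0.05, 0.10, 0.20 and 0.40 (effective N: 96%). The shortfall is small by ICC 0.02 (about 90 to 94%) and gone by 0.05.

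**Sensitivity to schedule mix**, all 28-day against all 21-day: 90% against 80% declared at true 0.10, ICC 0.1; 67% against 51% at true 0.20, ICC 0.05; false pass 38% against 40% at true 0.40, ICC 0. With 45 patients, 40% on 21-day and 10% dropping out, the same cells give 88%, 61% and 39%.

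**The case against.** The strongest reply concerns weight. The efficacy claim rests on the infection rate, and no stopping rule uses this limit. SAP section 10 says of the safety analyses that "The results will be descriptive in nature". The raw interval is reported alongside, so an impossible value would be noticed and a reader could recompute. All of that is true and limits the damage. But SAP 10.1.2 and protocol 10.4.3 still pre-specify a pass/fail declaration, and nothing else is tied to 0.4. The raw interval ignores clustering.

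A second reply is that step 4 errs on the safe side. Protocol 7.5 describes some patients as prone to infusion AEs, which points to a positive ICC, and from about ICC 0.05 the SAP limit does over-cover; the cost there is a missed declaration. This is half an answer: near ICC 0 the rule is lenient. Flooring DE at 1 and leaving step 4 otherwise alone would remove the leniency (false pass 2.7% or less) but would leave the pass rate at true 0.20, ICC 0.1 at 18%. The SAP's word conservative refers to the step 3 formula.

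Third, any clustering-adjusted limit lets the verdict depend on the ICC; at observed 0.35 the effective-N limit itself crosses 0.4 at an ICC of about 0.08. That is fair. The fault is that step 4 puts the crossing far too low.

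Last, protocol 2.3 cites 5 to 27.6% for related AEs in earlier trials. It counts related AEs only and does not say per patient or per infusion, so it is only a rough anchor. It does not rescue step 4, since observed proportions of 0.20 and 0.25 already fail above ICC 0.056 and 0.032.

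**Conclusion.** The concern holds. Step 4 is the operative definition of the limit compared with 0.4, it is wrong as written, and no other passage replaces it. The fault itself does not depend on any assumption; its size and direction do. They rest on the assumed ICC, AE proportion and schedule mix, none of which the documents supply for this rule. Across plausible mixes the pattern is the same: with moderate clustering an acceptable product will often fail, and with next to none a product at the threshold passes far more often than 5%. The ICC and DE formulas in steps 2 and 3 are not in dispute. Primary efficacy is untouched. The text should be corrected before database lock, because a change made once the results are known would look post hoc.

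**What to change.** Replace step 4 with: set DE = max(1, DE); take the Clopper-Pearson 1-sided 95% upper limit for x/DE events in N/DE infusions (the 0.95 quantile of a beta distribution with parameters x/DE + 1 and (N − x)/DE); this limit, over all infusions, is the one compared with 0.4. Its simulated coverage over the main grid was 91.5 to 96.4%, lowest at true 0.05 with ICC 0.3, far from the threshold. The floor is only a safeguard once effective N is used: false pass at true 0.40, ICC 0 is 4.0% with it and 5.0% without.

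As good practice, fix the GEE that both documents already mention (intercept only, logit link, robust standard error) as the sensitivity analysis, so that the choice is not left to the data review meeting.

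Cost: one line of SAP wording and programming, plus a sentence for the GEE. The protocol text can stand, since it does not say how the design effect is applied. No new data are needed.

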## 10.2. Treatment Compliance

Not applicable.

## 10.3. Adverse Events / Adverse Drug Reactions

Adverse events (AEs) will be coded using MedDRA to give a PT and a SOC term for each event. At the end of the study, AEs will be recoded applying the latest available MedDRA version available at this time point.

Adverse events temporally associated with the infusion are AEs occurring during infusion or within 72 hours after the end of infusion and are defined as infusional AEs.

Summary tables will be based on treatment-emergent adverse events (TEAEs), defined as those events with onset date/time at or after the first Klg10 infusion until the patient's last study visit.

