#### **4.8.2 DEATH**

For any patient withdrawn from study participation due to death, this should be noted on the Study Termination eCRF page, and the associated SAE that led to the death must be reported.

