## 6.9 UNSCHEDULED VISITS

During all the study periods, an unscheduled visit (non-routine study visit triggered by a specific event or for repetition of tests, e.g. Direct Coombs) may occur at Investigator's discretion and will be recorded in the source document and in eCRF.

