## 6.10 STUDY TERMINATION VISIT

The study termination visit will occur at week 51/52 (depending on treatment regimen). The termination visit is a clinic visit. The date of termination is the date of

the last contact in which the patients' health status is assessed or, in case where the patient does not agree to any further follow up, it is the date the consent is withdrawn. This date should be recorded on the termination CRF page.

Each patient will undergo the following tests and procedures:

- A physical examination (evaluation of all body systems and body weight) with an evaluation of vital signs (blood pressure, heart rate, and temperature).
- Collection of blood to measure IgG levels.
- Collection of blood samples for hematology, blood chemistry, and intravascular hemolysis testing.
- Collection of urine sample for urinalysis and intravascular hemolysis testing (urine hemosiderin).
- Collection of blood for a retention serum sample, for viral safety and possible future testing.
- Recording of all AEs and SAEs, including any infections, fever episodes, and hospitalization.
- Recording of concomitant medication, including use of antibiotics for any kind of infection.
- Review Patient Diary (with data collection).
- Record days off work/school/other major activities due to infections.
- Completion of QoL questionnaires (PedsQL™, and CCI [REDACTED]).
- Collection of other health care utilization information.

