6.2.7. Duration of Study

Duration of study = Date of termination – Date of first infusion + 1

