6.2.17. Prior/Concomitant medication

A medication is regarded as “prior” if the stop date of the event is prior to the date of first infusion, irrespective of the start date.

The medication is regarded as “concomitant” if the start date or stop date is between the date of first infusion (included) and the day of study termination (included).

The medication is regarded as “concomitant” if ticked as ongoing on the CRF.

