6.2.20. Study Duration/Length

Study Duration (in days) is computed as (Date of termination – Date of first infusion + 1)

This is equivalent to the definition of Day of Study Termination.

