6.2.21. Study Visit

Study Visit is the nominal visit as recorded on the CRF.

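### SAP 10.3 closes the TEAE window at the last study visit rather than at termination or death, so, read literally, an event starting after a patient's last recorded visit drops out of the TEAE serious and death rows.

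*SAP*

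**What the plan says.** SAP 10.3 builds the AE summary tables on TEAEs and defines these, by onset, as "those events with onset date/time at or after the first Klg10 infusion until the patient's last study visit". SAP 6.2.21 states: "Study Visit is the nominal visit as recorded on the CRF". The SAP contains no text that extends the TEAE window to termination, last contact or death.

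Other SAP periods end elsewhere. SAP 6.2.7 starts its formula with "Duration of study = Date of termination" and subtracts the date of first infusion; SAP 6.2.20 uses the same two dates. SAP 6.2.17 counts a medication as concomitant up to and including the day of study termination.

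Protocol 6.10 describes the termination visit as a clinic visit but gives the termination date its own definition: "the last contact in which the patients' health status is assessed", or the date of consent withdrawal if the patient declines further follow-up. For a patient who dies, Protocol 4.8.2 says that "this should be noted on the Study Termination eCRF page, and the associated SAE that led to the death must be reported". It does not mention a visit.

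The serious and fatal rows in SAP 10.3.1 and 10.3.2 are TEAE rows. The all-AE row in SAP 10.3.1 and the serious and fatal AE listings are not limited to TEAEs.

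**The concern.** The omission would depend on outcome. A patient who has an event between visits and then attends the next visit is counted. A patient who dies suddenly between the same two visits may not be, because the death is the reason that no later visit exists. The rows most exposed are therefore those for deaths and serious events.

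Late onset is foreseen: Protocol 2.3 asks for thrombosis monitoring in the weeks after an infusion as well as the first days. Two inconsistencies could follow. A drug given for the event could count as concomitant under SAP 6.2.17 while the event itself is not a TEAE. A fatal sepsis could also count towards the primary endpoint, which SAP 8.1.2 derives from AE data without a TEAE restriction, yet be absent from the TEAE death row.

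**Working it through.** The plan states no figure on this point, so there is none to reproduce. The check compares the rules and then bounds their effect.

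**1. The rules, by type of patient**

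- *Completer, or patient with an early termination visit recorded as a visit.* The last study visit is the termination visit. Protocol 9.2.4 also ends AE collection there. No gap.
- *Patient with a later unscheduled visit.* Protocol 6.9 says that such a visit "will be recorded in the source document and in eCRF". If it counts as a study visit, an event starting before it is a TEAE. No gap.
- *Patient who dies between visits.* The death goes on the Study Termination eCRF page and the SAE is reported. If that page is not a visit, the window closed at the previous visit.
- *Patient who withdraws or is lost between visits.* Protocol 6.11 asks for termination procedures only when possible and allows a telephone call. An event known from a diary, call or SAE report, with onset after the last recorded visit, falls outside the window.

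The rule works on onset, so an event that starts before the last visit and later proves fatal is counted.

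**2. A worked case (assumed dates, 28-day schedule)**

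The last recorded visit is week 16, day 16 × 7 + 1 = 113. A fatal event starts on day 130 and the patient dies on day 133. As written, 130 > 113, so it is not a TEAE. With the window extended to the date of death, 130 ≤ 133, so it is.

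**3. Uncovered time per patient**

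- One visit interval with its window: 21 + 3 = 24 days, or 28 + 4 = 32 days.
- Loss to follow-up after three consecutive missed visits (Protocol 4.8.4): 3 × 21 = 63 days up to 3 × 28 + 4 = 88 days.
- Longer if a withdrawn patient agrees to the safety follow-up in Protocol 4.8 and those contacts are not recorded as visits.

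**4. Number of patients and effect on a row**

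SAP 3.6 plans about 50 screened, with 10% screening failures and 10% dropouts. Taking both percentages of 50 gives about 45 treated, 5 dropouts and 40 completers. Five is a ceiling that assumes no dropout has a later recorded visit; the documents do not allow the real number to be derived.

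If one fatal event were affected (exact two-sided 95% intervals):

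- TEAE death row as written: 0/45 = 0% (0 to 7.9%).
- With the event counted: 1/45 = 2.2% (0.06% to 11.8%).

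**5. Share of follow-up**

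Assume that dropouts leave halfway.

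- All on the 21-day schedule: 40 × 357 + 5 × 178.5 = 15,172.5 patient-days.
- All on the 28-day schedule: 40 × 364 + 5 × 182 = 15,470 patient-days.
- One patient, one interval with window: 24/15,172.5 = 0.16%; 32/15,470 = 0.21%.
- One patient lost after three missed visits: 63/15,172.5 = 0.42%; 88/15,470 = 0.57%.

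Total AE counts would not visibly change. Only rows with very few events are sensitive.

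**The case against.** The strongest reply is that the last study visit simply means the termination visit. Protocol 4.2 runs participation through the last study visit and includes the termination visit in it, and Protocol 9.2.4 collects AEs until that visit. SAP 6.2.21 can be read as a labelling rule for by-visit tables, consistent with SAP 6.4, and SAP 10.3 does not cite it. Protocol 6.10 records the termination date on the termination CRF page, so a programmer could reasonably use that date. If the page counts as a visit, the gap disappears. The CRF is not in the documents, so this cannot be settled.

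This reply stands for every patient who has a termination visit. It does not settle the case of a patient who dies or leaves before one, because no text says where the window then closes.

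Stronger readings are tempting but unsupported:

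- *That deaths would be hidden.* They would not. The event stays in the all-AE row and the serious and fatal listings, and disposition shows the reason for premature termination, which includes death.
- *That disabling events in survivors would commonly be missed.* Protocol 9.2.6 wants any patient reporting an AE examined as soon as possible, and Protocol 4.8.1 requires AEs ongoing at withdrawal to be followed. A survivor will usually have a later recorded contact.
- *That a trial conclusion is at risk.* The primary endpoint does not use the TEAE window. The 0.4 rule in SAP 10.1.2 counts infusions with temporally associated AEs, which have their own 72-hour definition.

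A fair caution also applies to any remedy. Withdrawn patients may be followed for the rest of the study, so an extended window could label events long after the last infusion as treatment-emergent.

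**Conclusion.** The point holds as a minor defect of definition. Read literally, SAP 10.3 can leave a reported serious or fatal event out of the TEAE rows when it starts after the patient's last recorded visit, and the omission is related to outcome. This rests on two assumptions: that the Study Termination eCRF page does not count as a visit, and that no later contact is recorded as one.

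Probably 0 or 1 patients are affected. One affected death would change the TEAE death row from 1/45 to 0/45 and create a mismatch between the tables and the listings. SAP section 10 is descriptive, and no decision rule changes.

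**What to change.** In SAP 10.3, define TEAEs as events with onset from the first KIg10 infusion to the later of:

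- the last study visit, including unscheduled visits and early termination visits or calls;
- the date of termination as defined in Protocol 6.10.

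For a patient who dies before the planned termination visit, end the window at the date of death. This needs its own clause because the last health-status contact may precede the death. Show in the TEAE death row all deaths from the first infusion to that end date. Flag events with onset more than one dosing interval after the last infusion, so that late events in withdrawn patients can be identified.

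The cost is a short rewording of SAP 10.3, one line of derivation code and one flag. No new data are needed: the termination date and the SAE leading to death are already collected. The downside is that AE counts may rise slightly, and a few events in withdrawn patients may start well after the last dose, which is why the flag is needed.
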